10.4.5 Adherence and Retention Analyses

Data missingness will be assessed with descriptive statistics.

10.4.6 Baseline Descriptive Statistics

Baseline characteristics will be summarized with non-parametric statistics

10.5 Sample Size

The estimated sample size for the registry (500 participants) and the interventional trial (20 participants) are convenience samples based on the anticipated number of patients at NYU with COVID-19 infection. These numbers should provide sufficient power to conduct the regression analyses for the registry (up to 50 predictor variables), and for safety assessment of AT-001.

11 Source Documents and Access to Source Data/Documents

Source data is all information, original records of clinical findings, observations, or other activities in a clinical trial necessary for the reconstruction and evaluation of the trial. Source data are contained in source documents. Examples of these original documents, and data records include: hospital records, clinical and office charts, laboratory notes, memoranda, subjects' diaries or evaluation checklists, pharmacy dispensing records, recorded data from automated instruments, copies or transcriptions certified after verification as being accurate and complete, microfiches, photographic negatives, microfilm or magnetic media, x-rays, subject files, and records kept at the pharmacy, at the laboratories, and at medico-technical departments involved in the clinical trial. It is acceptable to use CRFs as source documents. If this is the case, it should

be stated in this section what data will be collected on CRFs and what data will be collected from other sources.

The study case report form (CRF) is the primary data collection instrument for the study. All data requested on the CRF must be recorded. All missing data must be explained. If a space on the CRF is left blank because the procedure was not done or the question was not asked, write "N/D". If the item is not applicable to the individual case, write "N/A". All entries should be printed legibly in black ink. If any entry error has been made, to correct such an error, draw a single straight line through the incorrect entry and enter the correct data above it. All such changes must be initialed and dated. DO NOT ERASE OR WHITE OUT ERRORS. For clarification of illegible or uncertain entries, print the clarification above the item, then initial and date it.

Access to study records will be limited to IRB-approved members of the study team. The investigator will permit study-related monitoring, audits, and inspections by the IRB/EC, the sponsor, government regulatory bodies, and University compliance and quality assurance groups of all study related documents (e.g. source documents, regulatory documents, data collection instruments, study data etc.). The investigator will ensure the capability for inspections of applicable study-related facilities (e.g. pharmacy, diagnostic laboratory, etc.).

Participation as an investigator in this study implies acceptance of potential inspection by government regulatory authorities and applicable University compliance and quality assurance offices.

12 Quality Assurance and Quality Control

QC procedures will be implemented beginning with the data entry system and data QC checks that will be run on the database will be generated. Any missing data or data anomalies will be communicated to the site(s) for clarification/resolution.

Following written SOPs, the monitors will verify that the clinical trial is conducted and data are generated, documented (recorded), and reported in compliance with the protocol, GCP, and the applicable regulatory requirements (e.g., Good Laboratory Practices (GLP), Good Manufacturing Practices (GMP)).

The investigational site will provide direct access to all trial related sites, source data/documents, and reports for the purpose of monitoring and auditing by the sponsor, and inspection by local and regulatory authorities.

13 Ethics/Protection of Human Subjects

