3.2 Secondary Objectives (if applicable)

- To develop predictive models of cardiac risk in hospitalized COVID-19 infection patients
- To assess safety of treatment with AT-001 plus standard of care on in-hospital survival in patients with COVID-19
- To characterize the effects of treatment with AT-001 plus standard of care on in-hospital mortality, progression of acute lung injury requiring mechanical ventilation, and serial measures of cardiac structure and function

4 Study Design and Endpoints

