4.2 Study Endpoints

4.2.1 Primary Study Endpoints

Primary Endpoint for Registry Study: Proportion of subjects with decreased left ventricular ejection fraction $\geq 10\%$ from baseline at time of hospitalization

Primary Endpoint for Embedded Clinical Trial: Safety of AT-001 based on adverse events reporting

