10.2 Statistical Hypotheses

The null hypothesis for the registry study is that there are no significant associations between clinical characteristics at study entry and subsequent occurrence of cardiac dysfunction, lung dysfunction or death in hospitalized patients with COVID-19 infection.

There will be no hypothesis testing for the interventional trial. The primary endpoint is safety of AT-001 based on descriptive statistics and qualitative evaluation of adverse event monitoring. Descriptive statistics will be used to assess frequency of secondary endpoints without hypothesis testing.

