10.4 Description of Statistical Methods

10.4.1 General Approach

Descriptive statistics will be used to define data missingness, data distributions.

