10.4.2 Analysis of the Primary Efficacy Endpoint(s)

Registry Study

CONFIDENTIAL This material is the property of the NYU School of Medicine and Langone Medical Center. Do not disclose or use except as authorized in writing by the study sponsor Interventional Template Version: 11 January 2019

- Multivariable logistic regression models and Cox Proportional Hazard models will be used to estimate the association between clinical variables at time of hospital admission and ICU admission with proportion of patients with decreased left ventricular ejection fraction ≥10% and secondary endpoints cardiac structure and function.
- Multivariable mixed models will be used to estimate the association between serial measures of cardiac structure and function, need for mechanical ventilation, and in-hospital mortality.

Interventional Study

- Safety assessment of AT-001 based on reported adverse events
- Exploratory analyses with descriptive statistics to estimate effects of co-enrollment on safety outcomes
- Exploratory analyses with descriptive statistics to describe clinical outcomes in patients treated

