10.4.3 Analysis of the Secondary Endpoint(s)

The same analyses will be used for secondary endpoints.

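### The claim in section 10.5 that 500 registry patients suffice for up to 50 predictors has no calculation behind it; if all 50 entered one unpenalised logistic model of the LVEF endpoint, it would be strongly overfitted

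*Combined protocol and SAP*

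**What the plan says.** Section 10.5 says that the 500 registry and 20 interventional participants "are convenience samples based on the anticipated number of patients at NYU with COVID-19 infection". The next sentence adds: "These numbers should provide sufficient power to conduct the regression analyses for the registry (up to 50 predictor variables". No alpha, power, effect size, event rate or allowance for missing LVEF accompanies it.

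The registry primary endpoint (section 4.2.1) is binary: "Proportion of subjects with decreased left ventricular ejection fraction" of at least 10% from baseline. Section 10.4.2 gives the analysis: "Multivariable logistic regression models and Cox Proportional Hazard models will be used to estimate the association between clinical variables" and this outcome. Mixed models are added for serial measures. For secondary endpoints section 10.4.3 says: "The same analyses will be used for secondary endpoints".

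The registry hypothesis concerns association: "The null hypothesis for the registry study is that there are no significant associations between clinical characteristics at study entry" and later cardiac dysfunction, lung dysfunction or death (section 10.2). Prediction is a secondary objective in section 3.2: "To develop predictive models of cardiac risk in hospitalized COVID-19 infection patients".

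On data quality, section 10.4.1 offers only this: "Descriptive statistics will be used to define data missingness, data distributions". Section 10 contains no rule for selecting predictors, for penalisation or for validation.

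**The concern.** In logistic regression, the number of parameters that the data can support depends mainly on the smaller outcome class, not on the total number of patients. A statement that 500 patients are enough for 50 predictors therefore needs an expected event rate and an expected number with evaluable LVEF. Neither is given.

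Prediction is what is at stake. A heavily overfitted model appears to discriminate in the data used to fit it and then gives risks that are far too extreme in new patients. Nothing in section 10 requires a check that would reveal this. An analyst who relies on section 10.5 could take a 50-predictor model to be adequately supported.

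**Working it through.** **Inputs from the documents.** N = 500 and up to 50 predictors (10.5). Binary LVEF endpoint (4.2.1). Logistic and Cox models (10.4.2). No LVEF event rate is stated. The nearest figure is about 10-20% for several cardiac complications together in severe disease, from reports in 41 patients (2.1); it is used only as a rough guide. Data come from the medical record (7.1.1), and the section 20 schedule lists no study echocardiogram, so LVEF may be missing for some patients.

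**The plan's own figure.** There is no power value to reproduce, because the inputs for one are absent.

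**Patients in the smaller class per predictor** = min(events, non-events) / predictors, with all 50 in one model and one parameter each:
- Ceiling: (500/2)/50 = 250/50 = 5.0. This needs a 50% event rate and all 500 evaluable.
- 10% events: 50/50 = 1.0. 20% events: 100/50 = 2.0.
- If only 60% (300 patients) had evaluable LVEF (assumed): 30/50 = 0.6, 60/50 = 1.2 and 150/50 = 3.0 at 10, 20 and 50%.

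**What such a model would do.** One unpenalised 50-predictor logistic model was simulated with independent standard normal predictors, 200 runs per setting and 10,000 new patients per run. The signal case has five true predictors with coefficients 0.5, 0.4, 0.3, 0.3 and 0.2. Event rates and coefficients are assumed.

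| n = 500 | 10% events | 20% | 50% |
|---|---|---|---|
| No signal: apparent AUC (new patients 0.50) | 0.79 | 0.72 | 0.68 |
| Signal: apparent AUC | 0.84 | 0.80 | 0.77 |
| Signal: AUC in new patients | 0.62 | 0.64 | 0.65 |
| Signal: calibration slope (ideal 1) | 0.24 | 0.37 | 0.47 |
| Signal, top 5% of predicted risk: mean predicted | 60% | 71% | 91% |
| Signal, same patients: observed | 20% | 39% | 76% |

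With 300 evaluable patients (assumed), apparent AUC with no signal rises to 0.87/0.79/0.74, and the slope with signal falls to 0.11/0.23/0.31.

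**Coefficients.** In a further simulation (300 runs per rate) with one true coefficient of 0.50 and 49 null predictors, the mean estimate was 0.610/0.577/0.573. The inflation is 0.610/0.50 = 1.22, 0.577/0.50 = 1.15 and 0.573/0.50 = 1.15, so about 15-22%.

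**How many parameters 500 patients might support.** Expected-shrinkage criterion, target S = 0.9: p = N(S − 1) ln(1 − R²/S), where R² is an assumed fraction of R²max = 1 − exp{2[π ln π + (1 − π) ln(1 − π)]} and π is the event rate. At π = 0.10, R²max = 0.478. With 15% of it, R² = 0.0717 and p = 500 × (−0.1) × ln(1 − 0.0717/0.9) ≈ 4. At 20% and 50% events, R²max is 0.632 and 0.75, giving about 6 and 7. If explained variation is 50% of its maximum, the figures are about 15/22/27. Neither assumption reaches 50.

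**The case against.** **Up to 50 is a ceiling and may describe a candidate pool.** This stands. The documents do not say that all 50 enter one model, so the limit of 5 and the simulated harm are conditional on that. Under the candidate-pool reading the adequacy claim is still unsupported, because no selection or validation rule is given.

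**The hypothesis and the methods text concern association; prediction is only a secondary objective.** This also stands. A reader might infer that the registry is underpowered to detect associations. The documents do not support that: they give no effect size or event rate from which power could be judged, and 500 patients could be adequate for a few pre-specified predictors.

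**Many of the registry regressions are not logistic.** Correct. The smaller-class limit does not apply to continuous changes in LVEF, diameters or biomarkers. Cox models depend on their own event counts, which are not given, and were not simulated.

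**The figures are hypothetical.** The event rates, coefficients, independence of predictors and 300 evaluable patients are all assumed. The ceiling of 5 needs no event rate.

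**A convenience sample in a pandemic registry is legitimate and openly declared.** Agreed. The objection is to the adequacy claim that follows it.

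**Conclusion.** The point holds in conditional form and should be fixed. Section 10.5 asserts sufficient power without the inputs that would support it. At its own upper limit of 50 predictors in one unpenalised logistic model of the LVEF endpoint, there would be at most 5 patients in the smaller class per predictor, and 1 to 2 on the rough 10-20% guide. Discrimination would then be badly overstated, with a calibration slope of roughly a quarter to a half under the assumed signal. Missing LVEF would make this worse.

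Two stronger readings should be avoided. One is that section 10.5 contains an arithmetic error: it contains no arithmetic. The other is that 500 patients are too few for the registry: nothing here shows that for models with few predictors or for continuous outcomes. The registry is observational, and the AT-001 safety analysis is not affected by this point.

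**What to change.** In 10.5, keep the convenience-sample sentence and replace the one after it with: *No power calculation was made for the registry regressions; the number of predictors in each model will be limited by the number of patients in the smaller outcome class (events for Cox models), as described in 10.4.2.* The clause on AT-001 safety assessment is outside this point and can stand as its own sentence.

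In 10.4.2, add:
1. The numbers with evaluable LVEF, and with and without a decrease of at least 10%, are tabulated before any modelling.
2. For binary and time-to-event outcomes, association and prediction models use a short predictor list ranked in advance on clinical grounds. The number of parameters is fixed from the tabulated counts before predictor-outcome associations are examined, for example by an expected-shrinkage criterion of 0.9 with the assumed explained variation stated.
3. If a larger candidate set is used for prediction, the model is penalised (ridge, LASSO or an equivalent shrinkage method).
4. Every prediction model is reported with cross-validated or optimism-corrected AUC or C and calibration slope, not apparent performance alone.

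A rule of one predictor per 10 events should not be offered as adequate in itself. In the simulated signal case with 5 predictors at 10% events, the slope was 0.86 when the list held the true predictors and 0.22 when it was drawn at random from the 50.

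The cost is wording, somewhat more analysis work, fewer or shrunken coefficients and a less favourable sample-size statement. The fix has limits. With few events, penalised slopes can be unstable: ridge at 10% events had a median slope of 1.27 but a mean of 3.3. For a badly chosen short list of 5 at 10% events, the bootstrap-corrected slope was still too favourable (0.58 against 0.24 in new patients), so the clinical ranking matters. These checks covered logistic models only.

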2.4 Potential Risks & Benefits

2.4.1 Known Potential Risks

In subjects enrolled in the prospective registry, the only risk is potential breach of confidentiality.

In subjects enrolled in the interventional trial, additional risk is associated with investigational agent. In the completed first in human study (Study AT-001.1001) AT-001 was generally well tolerated with no safety issues identified. There were no SAEs considered treatment-related and no AEs causing discontinuation of study treatment. No clinically relevant changes in vital signs, ECG or clinical safety laboratory values were noted.

Potential risks of AT-001 based on non-clinical data and previous experience with other aldose reductase inhibitors include:

- Acute hypersensitivity reactions
- Hepatic toxicity, including fatal hepatic necrosis
- Renal toxicity: Nephrolithiasis (calculi and pelvic dilation suggestive of an obstructive mechanism leading to development of pyelonephritis were reported in female rats in a 6-month chronic toxicology study. These renal findings were not reproduced in dogs in a 9-month chronic toxicology study)
- Gastrointestinal events, including nausea, vomiting, diarrhea, flatulence, abdominal pain
- Ocular effects (two cases of non-adverse, reversible multifocal pinpoint corneal opacities in a 28day toxicology study in dogs, which was not reproduced in a 9- month chronic toxicology study)
- Hypotension and dizziness
- Skin rash/eczema
- Decreases in hemoglobin, erythrocyte count, and lymphocyte count
- Reduction in total protein in blood

The incidence of these side effects for short-term exposure to AT-001 in COVID-19 patients is unknown. We anticipate that patients with COVID-19 infection will receive concomitant treatments including off-label use of FDA-approved drugs, anti-viral therapy with remdesivir under expanded access or emergency use access, and treatment with hydroxychloroquine, convalescent sera, and/or IL-6 inhibitors within the context of clinical trials. Based on knowledge of the pathophysiology of COVID-19 infection and the pharmacology of AT-001, we do not anticipate that these concomitant medications will increase risk associated with AT-001. Patients with COVID-19 infection are known to be a high risk of complications including

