5.6 Total Number of Participants and Sites

Recruitment will end when approximately 500 participants are enrolled in the registry, and approximately 20 participants in the interventional study.

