10.3 Analysis Datasets

The registry dataset consists of all subjects with any entered data. The interventional safety data set will be all subjects who received at least one dose of AT-001

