10.4.4 Safety Analyses

Adverse events will be analyzed as summary statistics and coded by MedDRA.

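### Section 10.5 claims sufficient power for the safety assessment of AT-001, but section 10.2 excludes any test and no rate or precision target is given, so that power is undefined for the primary endpoint

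*Combined protocol and SAP*

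**What the plan says.** Section 10.5 gives the basis for the trial's size: the registry and "the interventional trial (20 participants) are convenience samples based on the anticipated number of patients at NYU with COVID-19 infection". It goes on to say that these numbers should provide "sufficient power to conduct the regression analyses for the registry (up to 50 predictor variables), and for safety assessment of AT-001". Only the last clause, on the safety of AT-001, is at issue here; the registry clause is a separate matter.

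The rest of the plan for the interventional trial is descriptive:

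- Section 10.2: "There will be no hypothesis testing for the interventional trial". It adds: "The primary endpoint is safety of AT-001 based on descriptive statistics and qualitative evaluation of adverse event monitoring".
- Section 10.3: "The interventional safety data set will be all subjects who received at least one dose of AT-001".
- Section 10.4.4: "Adverse events will be analyzed as summary statistics and coded by MedDRA".
- Section 5.6 sets recruitment at "approximately 20 participants in the interventional study".
- Section 10.1 states that there is no formal SAP, so no other document supplies further detail.

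Section 2.4.1 lists potential risks drawn from non-clinical data and from other drugs of the class, among them "Hepatic toxicity, including fatal hepatic necrosis". It says that their incidence with short-term AT-001 in COVID-19 patients is not known.

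**The concern.** Power is the probability that a defined test rejects a defined null hypothesis under a defined alternative. Section 10.2 removes the test, and the documents supply neither a null nor an alternative. Section 10.5 therefore credits the design with a property that it does not have, and does so for safety, which section 4.2.1 makes the only primary endpoint of the interventional trial.

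At stake is what a reader or ethics committee takes from the sample-size section. They are told that the sample is adequate for the primary endpoint, yet no criterion of adequacy exists. If a particular harm does not appear among about 20 patients, nothing in the plan says how large a true incidence that result still allows.

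**Working it through.** **Reproducing the stated figure.** This is not possible. Section 10.5 gives no power value, and the documents contain no significance level, sidedness, reference rate, detectable difference or target interval width for safety. The only numerical safety rule is the halting rule in section 8.6. It carries no error rates and is not linked to the sample size.

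**What 20 patients can show.** The input from the documents is n = 20 (sections 5.6 and 10.5). Three things are assumed: all 20 are dosed and so enter the section 10.3 safety set, patients are independent, and confidence is 95%, since the documents name no level. The Protocol Summary calls the embedded trial randomised in one place, but sections 4.1 and 10 describe no allocation or control analysis, so all 20 are taken as treated.

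*Exact upper limit with zero events of a given type*, 1 − α^(1/n):

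- one-sided 95%: 1 − 0.05^(1/20) = 0.139, or 13.9%
- two-sided 95%: 1 − 0.025^(1/20) = 0.168, or 16.8%
- rule of three, as a rough check: 3/20 = 15.0%

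*Exact one-sided 95% upper limit with one event*: solve (1 − p)^20 + 20p(1 − p)^19 = 0.05, which gives p = 0.216, or 21.6%. The two-sided limit is 24.9%.

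*Chance of seeing at least one event*, 1 − (1 − p)^20:

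| True incidence p | Chance of at least one event in 20 |
|---|---|
| 1% | 18% |
| 2% | 33% |
| 5% | 64% |
| 10% | 88% |

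An 80% chance of seeing at least one event needs a true incidence of 1 − 0.2^(1/20) = 7.7%.

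**Sensitivity to the number dosed.** Recruitment is approximate. With 18 dosed, the zero-event one-sided limit is 1 − 0.05^(1/18) = 15.3%; with 22 it is 1 − 0.05^(1/22) = 12.7%. The conclusion does not depend on the exact count.

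**The case against.** The strongest reply is that nothing depends on the clause. Section 10.5 openly calls the sample one of convenience and hedges the power sentence. Sections 10.2, 10.4.2 and 10.4.4 promise only descriptive output. Safety is also judged case by case, through the daily and 7- and 14-day reviews in section 8.7 and the halting rule in section 8.6. Small early safety studies are normal.

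Most of this stands. It shows that the descriptive analysis is sound and that the fault lies in the justification. It does not rescue the sentence: the hedge still asserts a property that section 10.2 excludes, and neither case review nor a halting rule without error rates supplies power. Reading power loosely, as the chance of seeing a harm at all, does not help either, because that chance depends on an incidence that the protocol does not state and section 2.4.1 calls unknown.

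A reader might infer three stronger things that the documents do not support:

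- *That the trial rules out only serious-event rates above about 14%.* The figure applies to one type of event, with none observed, at one-sided 95% confidence. Section 8.7 expects many organ-dysfunction and septic-shock events from COVID-19 itself, so zero serious events overall is not a realistic result.
- *That a clean result will be reported as adequately powered evidence of safety.* No section plans that conclusion. The wording leaves room for it, but that is a risk and not a stated intention.
- *That a specific low power can be quoted against a background event rate.* The documents give no background rate and no test, so any such figure would be an invention.

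**Conclusion.** Section 10.5 is wrong as written on this point. It claims power for the safety assessment, section 10.2 excludes the test that power would require, and no other part of the protocol supplies an alternative criterion of adequacy. The claim is undefined rather than miscalculated.

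The precision that exists is modest. With 20 dosed, no event of a given type is compatible with a true incidence of up to 13.9% (one-sided 95%) or 16.8% (two-sided 95%), and an event with a true incidence of 1% would be missed entirely with probability 0.99^20 = 82%. These figures rest on the assumed 95% level and on 20 patients being dosed.

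The documents do not support the further inference that the trial is invalid or must be larger. A descriptive safety study in a convenience sample of this size is legitimate provided that its resolution is stated correctly.

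**What to change.** In section 10.5, delete the closing clause that extends the power claim to the safety of AT-001, and add:

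> No power is claimed for the interventional trial. If 20 patients are dosed, observing zero events of a given type gives an exact upper 95% limit of 13.9% one-sided (16.8% two-sided), and 21.6% one-sided after one event. The chance of observing at least one event with true incidence 1%, 5% or 10% is 18%, 64% or 88%. With 18 to 22 dosed patients the zero-event one-sided limit runs from 15.3% to 12.7%.

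In section 10.4.4, specify that serious adverse events, deaths and adverse event terms are each reported as patients with the event over the number actually dosed (the section 10.3 safety set), with exact 95% confidence intervals, and that safety conclusions are limited to that precision. The denominator should not be fixed at 20: recruitment is approximate, and section 5.7.2 deletes the data of participants who withdraw, so any dosed patient lost in that way should be disclosed beside the tables.

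The interval reporting goes a little beyond curing the contradiction, but it carries the stated precision through to the results. The change costs a few sentences, slightly more tabulation and a less favourable justification. It needs no extra patients or procedures and no change to dosing or to any clinical rule.
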